### **8.3.3 Prohibited concomitant therapies**

Between the start of the screening period and the end of the follow-up period, use of phototherapy to treat itching will be prohibited.

#### **8.3.4 Rationale for the prohibited concomitant medications, conditionally permitted concomitant medications, and prohibited concomitant therapies**

To exclude their effects on the efficacy evaluation of MR13A9.

### **8.4 Hemodialysis Conditions**

Between the start of the screening period and the end of the follow-up period, the frequency of dialysis per week and the hemodialysis method (HD, off-line HDF, on-line HDF, or I-HDF) may not be changed. Any temporary change in dialysis frequency or hemodialysis method associated with travel or admission to other hospitals with no changes in treatment strategies is acceptable. The hemodialysis conditions (duration of dialysis and dialyzer) should not be changed whenever possible.

### **8.5 Randomization and Blinding**

#### **8.5.1 Preparation and retention of a treatment assignment table**

The person responsible for treatment assignment will prepare a treatment assignment table and retain it until unblinding, as stipulated separately in the written procedure.

#### **8.5.2 Preparation and retention of emergency key codes**

The person responsible for treatment assignment will prepare emergency key codes to allow immediate identification of the treatment assigned to each subject in emergencies and retain them until unblinding, as stipulated separately in the written procedure.

#### **8.5.3 Subject registration**

##### **8.5.3.1 Primary subject registration**

The principal investigator or subinvestigator will assess the eligibility of all subjects providing consent at the time of signing informed consent (see “[5. Study Population](#)”), enter

---

necessary information in a primary subject registration form, and register the subjects by the next day.

The subject registration center will notify the principal investigator or subinvestigator about the acceptance or rejection of the primary subject registration for each subject.

#### **8.5.3.2 Secondary subject registration**

The principal investigator or subinvestigator will assess the eligibility of each subject at the start of the screening period (see “[5. Study Population](#)”), enter necessary information in a secondary subject registration form, and register the subject by the next day.

The subject registration center will notify the principal investigator or subinvestigator about the acceptance or rejection of the secondary subject registration of each subject.

For any subject eligible for primary registration but ineligible for secondary registration, the principal investigator or subinvestigator will notify the subject registration center about the reason for ineligibility.

#### **8.5.3.3 Tertiary subject registration**

The principal investigator or subinvestigator will assess the eligibility of each subject at the start of the double-blind period (see “[5. Study Population](#)”), enter necessary information in a tertiary subject registration form, and register the subject promptly.

The subject registration center will notify the principal investigator or subinvestigator about the acceptance or rejection of the tertiary subject registration of each subject, and the drug number for the subject when the registration of the subject has been accepted. The principal investigator or subinvestigator will prescribe the study drug of the drug number notified by the subject registration center for the subject.

For any subject eligible for secondary registration but ineligible for tertiary registration, the principal investigator or subinvestigator will notify the subject registration center about the reason for ineligibility.

#### **8.5.3.4 Registration for the extension period**

The principal investigator or subinvestigator will assess the eligibility of each subject at the start of the extension period (see “[5. Study Population](#)”), enter necessary information in a registration form for the extension period, and register the subject by the next day.

The subject registration center will notify the principal investigator or subinvestigator about the acceptance or rejection of the registration for the extension period of each subject.

For any subject eligible for tertiary registration but ineligible for registration for the extension period, the principal investigator or subinvestigator will notify the subject registration center about the reason for ineligibility.

#### **8.5.3.5 Randomization of subjects**

Based on the treatment assignment table prepared by the person responsible for treatment assignment, the subject registration center will randomly assign subjects eligible for tertiary registration to either the MR13A9 0.5 µg/kg or placebo group at a ratio of 1:1 by a dynamic allocation method using two stratification factors: Prior treatment with nalfurafine hydrochloride notified by the medical institution (for ≥ 2 consecutive weeks in the year prior

---

to the informed consent procedure) and specific signs or symptoms occurring during the screening period ([Appendix 4](#)) confirmed before dialysis on the start day of treatment.

### 8.5.4 Unblinding

The person responsible for treatment assignment will confirm that the blind has been maintained throughout the double-blind period and then unblind the treatment assignment table.

## 8.6 Sample size

### 8.6.1 Sample size

- Double-blind period

The study will enroll 86 subjects each MR13A9 0.5 µg/kg group and the placebo group (172 in total).

- Extension period

The study will enroll 100 subjects who complete 58-week treatment.

### 8.6.2 Rationale for the sample size

#### 8.6.2.1 Double-blind period

In a Japanese phase II clinical study (MR13A9-4), the change from baseline in the mean NRS score at Week 4 of the treatment period (mean  $\pm$  standard deviation) was  $-2.15 \pm 1.98$  in the placebo group and  $-3.22 \pm 2.09$  in the MR13A9 0.5 µg/kg group. The difference for the MR13A9 0.5 µg/kg group versus the placebo group at Week 4 of the treatment period was  $-1.04 \pm 0.35$  (adjusted mean  $\pm$  standard error).

For the primary variable of change from baseline in the mean NRS score at Week 4 of the double-blind period, its mean difference for the MR13A9 0.5 µg/kg group versus the placebo group was assumed to be  $-1.0$ , with a common standard deviation of  $2.0$ . Assuming a two-sided significance level of  $5\%$  and a statistical power of  $90\%$ , the sample size required to confirm the superiority of the MR13A9 0.5 µg/kg group to the placebo group using a two-sample t-test was calculated to be 86 subjects per group.

#### 8.6.2.2 Extension period

With reference to the “The Extent of Population Exposure to Assess Clinical Safety for Drugs Intended for Long-Term Treatment of Non-Life-Threatening Conditions” (ELD Notification No. 592 dated May 24, 1995), 100 subjects were assumed to complete 58-week treatment.

## 9. Subject Instructions and Management

The principal investigator or subinvestigator should sufficiently explain the significance and objectives of the study to subjects, and instruct and manage them especially for the following:

- 1) Confirm the absence of somnolence, dizziness, or similar symptoms after receiving the study drug and return home. Report any symptoms to the principal investigator or subinvestigator.

---

- 2) Pay attention during hazardous machine operation and automobile driving during the treatment period.
- 3) Maintain the symptom diary in subject every day. Report any device deficiencies to the principal investigator or subinvestigator.
- 4) Take all prescribed drugs other than the study drug properly as instructed.
- 5) Be sure to visit the study site as scheduled. Inform the study site in advance if it is impossible to visit for some unavoidable reason.
- 6) Visit the study site at the same time at every visit whenever possible during the study period.
- 7) Report the drug(s) used currently to the principal investigator or subinvestigator before participation in the study. Consult the principal investigator or subinvestigator about any new drug prescribed at other medical departments or hospitals or any over-the-counter drug before use. Report to the principal investigator or subinvestigator immediately if it was inevitable to use any drug without consultation.
- 8) Be sure to report in advance any visit to another department or hospital during the study period to the principal investigator or subinvestigator and report your participation in the study to the doctor at the department or hospital. If it is impossible to report in advance for unavoidable reasons such as an emergency visit, report your participation in the study to the doctor at the department or hospital and immediately report the visit to the department or hospital as well as prescribed drugs and other information to the principal investigator or subinvestigator.
- 9) Immediately inform the principal investigator or subinvestigator about any abnormalities in your body after undergoing tests at the end of the follow-up period or at the end of the follow-up investigation.
- 10) Women of childbearing potential must avoid intercourse or use appropriate contraceptive methods when having intercourse during the study period. Immediately inform the principal investigator or subinvestigator about any suspected pregnancy during the study period.
- 11) Men must avoid intercourse or use appropriate contraceptive methods when having intercourse. Immediately inform the principal investigator or subinvestigator about any suspected pregnancy of your partner between the start of study treatment and 12 weeks after the final dose.
- 12) Avoid disclosing any information related to this study, such as data used during the study, adverse events reported during the study, tests performed during the study, and personal remarks about administration of the study drug, on the Internet (e.g., Facebook, Twitter, blogs) or other information media (e.g., newspapers, magazines, advertisements).

## 10. Investigations, Observations, Tests, and Evaluations

The principal investigator, subinvestigator, and clinical research coordinator will perform investigations, observations, tests, and evaluations according to the study schedule and the following procedures.

### 10.1 Subject Demographics

The following subject demographics will be investigated and recorded in the case report form:

---

- 1) Date of written informed consent
- 2) Month of birth, sex, race
- 3) Body height
- 4) Etiology of chronic renal failure
- 5) Time when hemodialysis was started
- 6) Frequency of dialysis per week at the start of the screening period, hemodialysis methods (HD, off-line HDF, online HDF, I-HDF), and hemodialysis conditions (duration of dialysis, dialyzer)
- 7) Medical history (any concurrent disease at the time of signing informed consent); if yes, the name of the disease
- 8) Time of onset of itching associated with chronic renal failure
- 9) Prior treatment with nalfurafine hydrochloride between 1 year before the time of signing informed consent and the start of the screening period (Week -2); if yes, the duration of treatment and dose
- 10) Remaining renal function
- 11) Need for pregnancy testing
- 12) Information related to the inclusion/exclusion criteria
- 13) Specific signs or symptoms occurring during the screening period

## **10.2 Treatment Compliance**

Compliance with study treatment (day of dosing and route of dosing) will be recorded in the case report form. Also, the drug number and the dose of the study drug will be recorded in the case report form during the double-blind period and the extension period, respectively.

## **10.3 Dry Weight**

The dry weight before dialysis at Week -2, Week 6, and Week 34 will be recorded in the case report form.

## **10.4 Concomitant Medications and Concomitant Therapies**

### **10.4.1 Concomitant medications**

For all drugs (including over-the-counter drugs) used between the informed consent procedure and the end of the follow-up period, information on use (drug name, route of administration, duration of use, indication) will be recorded in the case report form. For any change in the drug name, dose, or dosing frequency of conditionally permitted concomitant medications, the date, detail, and reason for the change will be recorded in the case report form. The drugs listed below will require no recording in the case report form.

- Drugs used for dialysis (anticoagulants, local anesthetics, disinfectants, physiological saline used for priming and blood return, dialysate)
- Infusion solution used to establish access
- Diluents for injection

---

- Vehicles used for in-hospital dispensing (other than drugs of which main effect is expected)
- Pretreatment drugs for tests
- Nalfurafine hydrochloride used between the time of informed consent and the start of the screening period (Week -2)

#### **10.4.2 Concomitant therapies**

If phototherapy to treat itching is performed between the time of signing informed consent and the end of the follow-up period, implementation status of the therapy (name and duration of treatment) will be recorded in the case report form.

### **10.5 Implementation Status of Dialysis**

The dates of dialysis between the start of the screening period and the end of the follow-up period will be recorded in the case report form. For any change in the frequency of dialysis per week or the hemodialysis method (HD, off-line HDF, on-line HDF, or I-HDF), the date, detail, and reason for the change will be recorded in the case report form.

The sponsor will calculate the single-pool Kt/V at the start of the screening period. The single-pool Kt/V will be calculated using the Daugirdas formula.

### **10.6 Efficacy Endpoints**

#### **10.6.1 Symptom diary (electronic diary)**

The principal investigator, subinvestigator, or clinical research coordinator will instruct each subject on how to record the symptom diary, as well as register the information on each subject in the electronic diary system to prepare for the start of recording.

1) NRS score

Looking back on the period between the time of awakening on the previous day of assessment and the time of awakening on the day of assessment (including sleeping hours) once daily, subjects will assess the NRS score for the most severe itching by themselves and record the score in the symptom diary. According to [Appendix 1](#), the most severe itching within the day will be recorded in integers on a scale ranging from 0 to 10, where 0 represents no itching and 10 represents worst itching imaginable.

2) Shiratori's severity criteria

Looking back on the period between the time of awakening on the previous day of assessment and the time of awakening on the day of assessment (including sleeping hours) once daily, subjects will assess the degree of itching by themselves and record the score in the symptom diary. According to [Appendix 2](#), the symptoms during the day and the night will be recorded on a scale ranging from 0 to 4, where 0 represents no symptoms and 4 represents severe itching.

#### **10.6.2 Skindex-16**

At the first visit (before dosing of the study drug) of each week (Monday or Tuesday), subjects will look back on the condition of itching in the past week and assess how often they were bothered by itching. According to [Appendix 5](#), the frequency of itching will be recorded

---

based on a scale ranging from 0 to 6, where 0 represents never bothered and 6 represents always bothered. The date of recording and the result will be recorded in the case report form.

### **10.6.3 5-D itch scale**

At the first visit (before dosing of the study drug) of each week (Monday or Tuesday), subjects will look back on the condition of itching in the past 2 weeks and record the 5 components of itching (duration, degree, direction, disability, distribution) according to [Appendix 6](#). The date of recording and the result will be recorded in the case report form.

### **10.6.4 PGIC**

At the first visit of each week (Monday or Tuesday), subjects will compare the overall symptom of itching with the symptom in the screening period, and record it on a 7-level scale consisting of very much improved, much improved, minimally improved, no change, minimally worsened, much worsened, and very much worsened, according to [Appendix 7](#). The date of recording and the result will be recorded in the case report form.

## **10.7 Laboratory Tests**

Blood samples will be collected for the tests listed below before the first dialysis of each week (Monday or Tuesday). Laboratory test values will be determined centrally at the laboratory testing facility. The presence or absence of collected samples will be recorded in the case report form.

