## Study Schedule

Visit (weeks after initial dose)	Screening period			Double-blind period						Extension period							Follow-up period	
	Week -2	Week -1	Initial dose	Week 1	Week 2	Week 4	Week 6	Week 7	Week 8	Week 10	Week 12	Week 18	Week 26	Week 34	Week 46	Week 58	Week 59	
Acceptable time window a)	—	—	—	—	—	—	—	—	—	—	—	Week 17–19	Week 25–27	Week 33–35	Week 45–47	Week 57–59	—	
Visit	1	—	2	3	4	5	6	7	8	9	10	11	12	13	14	15	16	
Day of the week a)	Mon/Tue	Mon/Tue	Mon/Tue	Mon/Tue	Mon/Tue	Mon/Tue	Mon/Tue	Mon/Tue	Mon/Tue	Mon/Tue	Mon/Tue	Mon/Tue	Mon/Tue	Mon/Tue	Mon/Tue	Mon/Tue	Mon/Tue	
Informed consent	●																	
Eligibility assessment	●	●		●			●											
Subject demographics	●	●		●														
Subject registration	Primary	Secondary		Tertiary			Entering into the extension period											
Study treatment b)				—													→	
Confirmation of DW/dose	●						●								●			
NRS c)	—																→	
Shiratori's severity criteria c)	—																→	
Skindex-16 5-D itch scale			●			●				●		●	●	●	●	●	●	
PGIC					●					●		●	●	●	●	●	●	
Vital signs d)	●		●	●	●	●	●	●	●	●	●	●	●	●	●	●	●	
Laboratory tests d)																		
Postdialysis BUN	●																	
Postdialysis weight																		
Serum pregnancy test e)	●																●	
Body weight d)	●		●				●				●			●		●	●	
12-lead ECG d)																		
Dependency assessment												● d)		● d)		● d)	●	
Adverse events																		
Concomitant medications/therapies	—																→	
Specific signs/symptoms		—															→	
Prohibited concomitant medications																		
Prohibited concomitant therapies			—														→	
Hemodialysis method																		
Conditionally permitted concomitant medications			—														→	

a) Assessments and tests will be performed on the day of first dialysis of each week (Monday or Tuesday).

b) The study drug will not be administered in Week 58.

c) Subjects will record these data in the symptom diary once daily from the next day of the start date of the screening period until the end of the follow-up period.

d) To be performed before dialysis.

e) To be performed only in women of childbearing potential (within 1 year of their last menstrual period and who have not undergone hysterectomy or bilateral total ovariectomy).

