## Study Schedule (at the time of discontinuation)

	Double-blind period or extension period	Follow-up period f)
Visit (weeks after initial dose)	At discontinuation	Week 1 after discontinuation
Visit	—	—
Day of the week	— e)	— g)
Informed consent		
Eligibility assessment		
Subject demographics		
Subject registration a)	●	
Study treatment		
Confirmation of DW/dose		
NRS b)		
Shiratori's severity criteria b)		→
Skindex-16	●	
5-D itch scale		
PGIC	●	
Vital signs c)	●	
Laboratory tests c)		
Postdialysis BUN		
Postdialysis weight		
Serum pregnancy test d)	●	
Body weight e)	●	
12-lead ECG e)		
Dependency assessment	● c)	●
Adverse events		
Concomitant medications/therapies		→
Specific signs/symptoms		→
Prohibited concomitant medications		
Prohibited concomitant therapies		→
Hemodialysis method		
Conditionally permitted concomitant medications		→

a) To be performed only in subjects withdrawing from the study during the double-blind period.

b) Subjects will record these data in the symptom diary once daily until the end of the follow-up period.

c) To be performed before dialysis.

d) To be performed only in women of childbearing potential (within 1 year of their last menstrual period and who have not undergone hysterectomy or bilateral total ovariectomy).

e) Assessments and tests will be performed on the next dialysis day after discontinuation has been decided.

f) Excluding those withdrawing from the study during the screening period.

g) To be performed on the same day of the week as the day of the assessments at discontinuation.

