### **5.3.2 Responses to the discontinuation of any individual subject**

- If a subject meets any of the criteria described in “[5.3.1 Discontinuation criteria \(discontinuation of individual subjects\)](#)” during the study, the principal investigator or subinvestigator will immediately decide to discontinue the study. On the next dialysis day after the decision to discontinue, the prespecified assessment items at discontinuation will be measured and assessed and the date of discontinuation and the reason for discontinuation will be recorded in the case report form. The date of discontinuation will be the day when the principal investigator or subinvestigator decides to discontinue the study. If the study is discontinued during the double-blind period or the extension period, the next day of the assessments at discontinuation will be regarded as the start date of the follow-up period.
- If the study is discontinued because of the occurrence of an adverse event, the principal investigator or subinvestigator will promptly provide appropriate treatment for the subject and perform a follow-up investigation, as instructed in “[10.13.9 Follow-up investigation](#).”
- If a subject does not return to the study site, the principal investigator, subinvestigator, or clinical research coordinator will immediately investigate the reason for missed visits and the subsequent course.

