## **10.9 Body Weight**

Body weight will be measured before the first dialysis of each week (Monday or Tuesday). The date and result of measurement will be recorded in the case report form. At the start of the screening period, body weight will also be measured after dialysis, and the date and result of measurement will be recorded in the case report form.

---

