5.7.2 Handling of data in tabulation at the final assessment point

- In the double-blind period, efficacy data (Skindex-16, 5-D itch scale, and PGIC) obtained at Weeks 1 to 4 (or at the time of withdrawal during the double-blind period before Week 4) and safety data obtained at Weeks 1 to 6 (or at the time of withdrawal during the double-blind period) will be included in the tabulation. Data for observations and tests performed at the latest time point within 10 days after the day of the final dose during the double-blind period will be used as the data at the end of the double-blind period. Data for observations and tests performed at unscheduled visits will be excluded from the tabulation.
- For the entire study period, data from Weeks 1 to 58 (or at the time of withdrawal during the extension period) will be included in the tabulation. Data for observations and tests performed at the latest time point within 10 days after the day of the final dose during the extension period will be used as the data at the end of the extension period. Data for observations and tests performed at unscheduled visits will be excluded from the tabulation.

6. Statistical/Analytical Issues**6.1 Adjustments for Covariates**

The change from baseline in the mean NRS score at Week 4 of the double-blind period, the primary variable, will be analyzed using the baseline mean NRS score and the presence of prior treatment with nalfurafine hydrochloride, a dynamic allocation factor, as a covariate. For details, refer to "[11.1.1 Primary variable](#)." If an imbalance is observed in the subject demographics of the FAS, the primary analysis set for efficacy, a supplementary analysis will be performed with

additional items showing the imbalance as the covariates in the primary analysis.

For the changes from baseline in the itch score based on the Shiratori's severity criteria, changes from baseline in Skindex-16, and changes from baseline in 5-D Itch Scale, an analysis will be performed using the baseline as a covariate for each item. Details are shown in "[11.2.1.1 Change from baseline in the mean itch score](#)," "[11.2.2.1 Changes from baseline in Skindex-16](#)," and "[11.2.3.1 Changes from baseline in 5-D itch scale](#)," respectively.

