12.2.2 Shift table of laboratory data

The numbers and percentages of subjects with values (low, normal, or high) before and after treatment will be presented.

The assessment time points are as follows:

- Double-blind period: Baseline and at the end the double-blind period
- Entire study period: Baseline and at the end of the extension period

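### End-of-period laboratory and weight tables set first-dialysis-of-the-week baselines against withdrawal values that often follow a shorter interdialytic gap, with no flag for the difference

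*Protocol*

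**What the plan says.** **Scheduled visits.** Protocol 10.7 states: "Blood samples will be collected for the tests listed below before the first dialysis of each week (Monday or Tuesday". Protocol 10.9 states: "Body weight will be measured before the first dialysis of each week (Monday or Tuesday". Footnote a) of the Study Schedule applies the same rule to every planned visit, including baseline and Week 6: "Assessments and tests will be performed on the day of first dialysis of each week (Monday or Tuesday".

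**Discontinuation.** Footnote e) of the discontinuation schedule reads: "Assessments and tests will be performed on the next dialysis day after discontinuation has been decided". Protocol 5.3.2 agrees: "On the next dialysis day after the decision to discontinue, the prespecified assessment items at discontinuation will be measured and assessed". Neither sets a weekday, and 10.7 and 10.9 mention no exception. Protocol 11.18 lists laboratory tests and pre-dialysis weight among the discontinuation assessments.

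**Analysis.** SAP 5.7.2 includes withdrawal data and defines the end-of-extension value by "Data for observations and tests performed at the latest time point within 10 days after the day of the final dose during the extension period". The double-blind rule is parallel. The laboratory shift tables (SAP 12.2.2) use, for the long-term data, "Entire study period: Baseline and at the end of the extension period". The scatterplots (12.2.3, 12.3.2) make the same comparison, and the summary statistics (12.2.1, 12.3.1) have an end-of-period column. Nothing separates values by position in the dialysis week.

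**Data available.** Protocol 10.5: "The dates of dialysis between the start of the screening period and the end of the follow-up period will be recorded".

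**The concern.** Solutes cleared by dialysis, and fluid weight, build up between sessions. A sample taken after the longest gap of the week will on average be higher than one taken after a shorter gap in the same patient. Completers are compared like with like, because baseline and the final visit both precede the week's first dialysis. Withdrawn subjects often are not. Their BUN, creatinine, potassium, phosphate and pre-dialysis weight would tend to fall from baseline to end of period simply because the sampling day changed.

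At stake is the reading of descriptive safety tables. In the open-label extension no concurrent control arm could reveal the artefact. In the double-blind period it would follow any difference in withdrawal between the arms.

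**Working it through.** The plan gives no figure on this point to reproduce. The check covers the calendar, the 10-day rule and the size.

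**1. Share of discontinuation tests after a short gap.** Dialysis is three times weekly (protocol 5.1.1). The weekdays are not stated. I assume Mon/Wed/Fri or Tue/Thu/Sat, with gaps of 2, 2 and 3 days; both patterns give the same shares. Each decision day is mapped to the next session:

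- Mon or Tue leads to Wed, and Wed or Thu leads to Fri: 2-day gap.
- Fri, Sat or Sun leads to Mon: 3-day gap.
- Decisions even over 7 days: 4/7 = 57% short.
- Decisions even over the three dialysis days: 2/3 = 67% short.
- All decisions at the week's first-dialysis visit: 100% short.
- All decisions from the week's last session to the day before the next first session: 0% short.

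**2. Which values pass the 10-day rule.** Suppose withdrawal is decided at the last of k consecutive missed doses and tests follow at the next session:

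- k = 0 to 3: 2 to 10 days after the final dose, so used.
- k = 4 (double-blind discontinuation criterion): 11 to 12 days, so excluded.
- k = 7 (extension criterion): 18 to 19 days, so excluded.

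**3. Size for one BUN value.** Assumptions: linear accumulation at rate g; intervals of 68 h (long) and 44 h (short); urea reduction ratio U of 65 to 75%. With r = 1 − U, the steady weekly cycle of pre-dialysis levels (L at the first session, then W, then F) satisfies

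W = rL + 44g, F = rW + 44g, L = rF + 68g,

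so L = g[68 + 44(r + r²)] / (1 − r³).

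- U = 65% (r = 0.35): L = 88.79/0.9571 = 92.8g, W = 76.5g, F = 70.8g. W/L = 0.824 and F/L = 0.763. The mean fall is 20.6%.
- U = 75% (r = 0.25): L = 81.75/0.9844 = 83.0g, W = 64.8g, F = 60.2g. W/L = 0.780 and F/L = 0.725. The mean fall is 24.8%.

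For weight, the shortfall is (68 − 44)/68 = 35% of the long-gap gain, or 0.7 to 1.4 kg for an assumed gain of 2 to 4 kg. Creatinine, potassium and phosphate are not quantified.

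**4. Shift in the column mean.** Shift = proportion withdrawn × short-gap share × fall per value.

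- 10% withdrawn (assumed): from 0.10 × 4/7 × 20.6% = 1.2% to 0.10 × 2/3 × 24.8% = 1.7%.
- Ceiling for the extension: the plan has 172 randomized and 100 completing 58 weeks. The entire-study groups contain only extension entrants (protocol 14.2.2). If 10 to 20 subjects leave before Week 6 (assumed), non-completers are 62/162 = 38% to 52/152 = 34%. The shift runs from 0.342 × 4/7 × 20.6% = 4.0% to 0.383 × 2/3 × 24.8% = 6.3%.

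**5. A concrete case.** A subject refused entry to the extension at Week 6 already has a first-dialysis sample from that visit. The discontinuation test at the next session is later and within 10 days, so under SAP 5.7.2 it displaces the matched sample. SAP 5.7.1 prefers the scheduled visit when several values fall in one window; 5.7.2 has no such preference.

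**The case against.** Prompt testing at withdrawal with a last-available-value rule is a defensible choice, because it keeps the sample closest to the event that led to withdrawal. The outputs are descriptive, with no test or decision rule attached. By-visit summaries are planned as well, laboratory adverse events rest on the investigator's judgement (protocol 10.13.1.3), and abnormal values are listed by subject (SAP 12.6). All of this stands and keeps the point minor.

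The same argument rules out a stronger remedy that a reader might infer, namely replacing each withdrawal value with the last matched first-dialysis sample. After Week 12, laboratory visits are at Weeks 18, 26, 34, 46 and 58, so the substitute could be about 12 weeks old. Extension weights are at Weeks 6, 12, 34 and 58, so a substitute weight could be about 24 weeks old. Weight in the double-blind period is taken only at Week −2, baseline and Week 6, so an earlier withdrawal would have no post-baseline weight.

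A reader might also take 72/172 = 42% as the proportion affected. The documents do not support that. It counts double-blind withdrawals who are not in the extension tables, and it treats an exposure target (protocol 8.6.2.2) as a dropout forecast. Some non-completers will also supply no usable value, because they fall outside the 10-day rule or are lost to follow-up.

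What the objection does not answer is that matched and unmatched values share one column without a flag, although the dates needed to separate them are collected.

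**Conclusion.** The timing mismatch is real and documented, and it pushes gap-dependent measures downward in withdrawn subjects. It is a minor point: the primary analysis is untouched and completers' values are matched.

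Its size rests on assumptions outside the documents: the 2/2/3-day pattern, even decision days, 68 h and 44 h intervals, linear accumulation, the urea reduction ratio and the withdrawal rates. On these, a short-gap BUN is about 21 to 25% lower. The column mean moves by roughly 1 to 2% at 10% withdrawal. The 4 to 6% range is a ceiling, not an expectation. The sponsor can replace the assumed reduction ratio with its own, which SAP section 7 already derives.

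A reader might infer that the shift tables will show spurious moves from high to normal. That is possible for individual subjects, but the documents give no reference ranges or baseline levels from which to count them.

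**What to change.** In SAP 5.7.2 and 12.2 to 12.3:

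- Keep the planned end-of-period value, and derive the time since the previous session from the recorded dialysis dates.
- For BUN, creatinine, potassium, phosphate and pre-dialysis weight, show end-of-period values not taken before the week's first dialysis in a separate row (summaries, shift tables) or with a separate symbol (scatterplots).
- Where a scheduled first-dialysis sample from the same week also lies within the 10-day window, as in the Week 6 case, use that sample in the main row.
- Do not replace withdrawal values with samples from earlier weeks. All other analytes stay as planned.

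Protocol 10.7 and 10.9 should also be reconciled with 5.3.2 and footnote e) of the discontinuation schedule, so that the timing of discontinuation tests is stated consistently.

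The cost is one derived variable from data already collected, a few lines of SAP text, and small extra rows in descriptive tables.
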